### 3.13 Loss to Follow-up

A participant will be considered lost to follow-up if they discontinue the intervention or are unable to be contacted by the study site staff.

The following actions must be taken if a participant fails to return to the clinic for a required study visit:

- As this is a pragmatic trial, the clinic will follow standard clinical operating procedures for missed appointments.

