## 2.8 Inclusion and Exclusion Criteria

*Cross-reference: UNC IRBIS Application: A.2.7 (age range), A.3.1 (inclusion and exclusion criteria), A.4.2*

To be eligible to participate in this study, an individual must meet all the following criteria:

- Aged 18 to 85 years
- History of CNCP
- Receiving high-dose COT for chronic non-cancer pain (CNCP) as evidenced by current or most recent prescription of an average daily morphine-equivalent dose (MED) of 20 mg or greater for CNCP. Specific opioid analgesics are noted in Section 3.
- Receiving care at a participating clinic from a participating provider, as evidenced by at least 1 in-person visit within the past 12 months

Participants must be using at least 20 mg daily MED to be eligible for the study. If MED data are not available via the institution's data warehouse, a proxy of 3 or more opioid prescriptions to treat chronic pain within the past 12 months may be used to identify these patients in the prescreening phase. However, we will confirm in the EHR that the actual dosage prescribed is at least 20 mg daily MED. Because patients will be taking various opioid medications, daily opioid dose will be standardized to daily MED using standard opioid conversion tables.

An individual who meets any of the following criteria will be excluded from participation in this study:

- Not meeting the above inclusion criteria
- Opioid use is for pain directly related to an active cancer diagnosis
- Opioid use is for maintenance treatment of an opioid use disorder (OUD)
- Suicide attempt within the past 3 years
- Active suicidal ideation
- Currently receiving CBT
- Non-English speaking
- Other reason at the discretion of the investigator

Self-report screening items that are not ascertained via medical record data are provided in the **Participant Screening and Consent Script** (see attached).

Two exclusion criteria pertain to past medical history: a) If the patient does not have a history of chronic non-cancer pain, they will be excluded; b) if the patient has a history of suicide attempt within the past 3 years, they will be excluded. There is no exclusion based on accidents or injury.

Patients may be excluded for a limited set of other reasons based on the investigator's discretion. It is difficult to anticipate the rare, often unique types of situations in which a patient may not be fit for the intervention and to develop specific exclusion criteria for each hypothetical instance.

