### 3.12 Withdrawal from the Study

*Cross-reference: UNC IRBIS Application section A.7.3.*

Participants are free to withdraw from participation in the study at any time upon request. An investigator may discontinue or withdraw a participant from the study for the following reasons:

- If any adverse event (AE) or other medical condition or situation occurs such that continued participation in the study would not be in the best interest of the participant.
- Disease progression that requires discontinuation of the study intervention.
- If the participant meets an exclusion criterion (either newly developed or not previously recognized) that precludes further study participation.

The reason for participant discontinuation or withdrawal from the study will be recorded in the Enrolled Participant Database. The study will retain participant data collected prior to withdrawal. We will not contact the participant to obtain any more self-report data, and the participant will not receive any further intervention. However, if the participant has completed any part of the intervention, we would like to continue to extract the participant's EHR data, and we will use the **Withdrawal Consent Addendum** (see Appendix) to seek permission to do so. If the participant withdraws prior to participating in the intervention, we will not collect any more of their data.

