4.6 Database Lock

As noted above, 3 different study databases will provide data. The last participant is expected to be enrolled in March 2022 and the last intervention visit may go until March 2023. The last T2 (6-month) survey is expected in September 2022 and the last T3 (12-month survey) is expected in March 2023. The T2 and T3 survey database will be locked approximately one month after the last completion of the T3 survey. The REDCap database lock will occur after the last participant's final intervention status CRF has been completed (i.e., completed the 12-month intervention phase) and all data queries have been resolved by the study sites. As mentioned above in section 4.4.3, the EHR data extraction takes places 3 times across the study. *Although the final EHR data extraction is planned to take place in July or August 2023, or 18-months after the last participant was enrolled into the study, it will likely not contain 18-months of EHR data for the last participant since there is up to a 3-month lag between clinic visit and data inclusion in the CDM. However, all participants should contain 12-months of EHR data in the final extraction (the study's primary timepoint).* The final EHR data extraction will be considered final and locked after the sites have addressed any potential RTI queries and transferred a clean dataset (expected to occur ~2-months after the initial data transfer). The locked datasets from each of the 3 databases will be used to derive the final analysis dataset which will be used to perform the analyses described within this SAP. Analysis data specifications are further described in section 9.2.

The study is designed as intention-to-treat (ITT). If a participant discontinues further intervention or participation in the study, every attempt will be made to continue to perform the required study-related follow-up surveys and EHR data extraction. However, surveys and EHR data will not continue to be collected from those who are determined ineligible, withdrew from all study activities, investigator withdrew and other (depending on the reason).

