8. STUDY PARTICIPANT CHARACTERIZATION

8.1 Participant Disposition

Participant eligibility status and disposition will be summarized and described using a standard CONSORT diagram. The diagram will include the number of participants randomized, the

number completing any intervention visits, the number that did not actively withdraw from the study, survey completion rates, and participants with EHR data extraction. Due to the pragmatic nature of the study, many participants may have been marked as completing the intervention phase of the study; however, they did not actually complete any intervention visits and could not be contacted by research coordinators. However, these participants were still included in the study as they received survey invitations and EHR extractions. For CONSORT reporting purposes under the study follow-up section, we will report the number and percentage of those that did NOT actively withdraw or discontinue early and the summary statistics for those that did withdraw or discontinue early. Among those that definitively ended the study early, reasons for study discontinuation or withdrawal will be listed.

In the event a participant is accidentally randomized twice, the participant's first randomization assignment will only be displayed and included in the ITT analyses. The participant's second randomization assignment will be removed from the analysis dataset and subsequent data analyses.

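### Protocol 3.13 counts stopping the intervention as loss to follow-up, and Protocol 3.12 with SAP 4.6 ends outcome collection after investigator withdrawal, against the intention-to-treat plan

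*Protocol*

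**What the plan says.** **Definition of loss to follow-up.** Protocol 3.13: "A participant will be considered lost to follow-up if they discontinue the intervention or are unable to be contacted by the study site staff". Its only listed action is to follow the clinic's usual procedure for missed appointments. Protocol 3.9.2 treats loss to follow-up differently, as the end point of tracing and recontact.

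**Withdrawal.** Protocol 3.12 lets an investigator withdraw a participant for an adverse event, for disease progression that obliges the intervention to stop, or on this ground: "If the participant meets an exclusion criterion (either newly developed or not previously recognized) that precludes further study participation". After withdrawal, "We will not contact the participant to obtain any more self-report data, and the participant will not receive any further intervention". EHR extraction may continue with a signed addendum if some of the intervention was completed; otherwise, "If the participant withdraws prior to participating in the intervention, we will not collect any more of their data".

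**SAP.** Section 4.6 says that when a participant discontinues the intervention or the study, "every attempt will be made to continue to perform the required study-related follow-up surveys and EHR data extraction". Its next sentence makes exceptions: "surveys and EHR data will not continue to be collected from those who are determined ineligible, withdrew from all study activities, investigator withdrew", and some others depending on the reason. Section 8.1 describes participants who had no intervention visits and could not be reached: "However, these participants were still included in the study as they received survey invitations and EHR extractions".

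**Analysis.** Protocol 5.1 and SAP 5.1 analyse everyone as randomised, whatever intervention was received.

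**The concern.** An intention-to-treat analysis needs outcomes from people who stop treatment. The documents blur two events that should be kept apart: the intervention ending and measurement ending.

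Protocol 5.1 expects missed CBT sessions and leaving the SDM provider to be the commonest nonadherence. A site that applies 3.13 literally would record these people as lost to follow-up while they are still being surveyed, so the term would describe attendance instead of missing outcomes.

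The more serious part is investigator withdrawal, where the written rules do end collection. Three kinds of data depend on the T2 and T3 surveys:

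- **PROMIS.** Both key secondary outcomes come only from surveys. Protocol 5.3.3 accepts that attrition may be related to opioid use, function and pain interference. The SAP 9.4 tipping-point analysis covers the primary outcome only, and only if that result is significant and more than 20% of 12-month MED is missing. PROMIS has no analysis under missing-not-at-random assumptions.
- **Opioid dose.** Under SAP 9.2, days after the last prescription count as zero MED only if survey item G20 is answered in the negative; otherwise they are missing. With no survey, a true zero becomes a missing value. The 12-month discontinuation outcome in SAP 9.6.3 also rests on T3.
- **Safety.** Surveys are one of the sources in Protocol Table 11. Protocol 8.3.5 picks up suicide risk when it surfaces at an intervention visit, and withdrawal under 3.12 ends those visits too.

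**Working it through.** **1. The rules side by side**

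| Situation | Protocol | SAP |
|---|---|---|
| Stops attending, does not withdraw | 3.13: lost to follow-up. 3.9.2: lost only after tracing fails. 9.3: surveys are timed from randomisation, with no link to attendance | 4.6: surveys and EHR continue. 8.1: people with no visits were still invited and extracted |
| Investigator withdraws, some intervention completed | 3.12: surveys end; EHR continues if the addendum is signed | 4.6: surveys and EHR both end |
| Participant withdraws before any intervention | 3.12: nothing more is collected | 4.6: nothing more, if withdrawn from all activities |

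Row 1 is a conflict of definition. In row 2 the documents agree that surveys end and disagree on EHR, and ending collection fits poorly with intention to treat. Row 3 shows no conflict where the participant leaves all study activities.

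**2. The plan's own power figures**

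Inputs from SAP 6: differences 3.5 (pain interference) and 2 (physical function), SD 10, 1:1 allocation. Two-sided alpha is 0.05. Power = Φ(δ / (σ√(2/n)) − 1.96), with n per arm.

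- Planned: 608 × 0.75 = 456, n = 228. Pain interference: 3.5/0.937 = 3.74, power 96.2%. Physical function: 2/0.937 = 2.14, power 57.0%. The stated 96% and 57% reproduce. (SAP 6 gives 20% missing; the figures then need the design effect of 1.07 and come to 96.2% and 56.8%.)
- Post hoc: design effect 1 + (8 − 1) × 0.01 = 1.07. 526 × 0.60 / 1.07 = 295, giving 85.2% and 40.4%. The stated 85% and 40% reproduce.

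**3. How many participants could be affected**

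SAP 6 reports 20% study discontinuation and about 40% missing surveys.

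- Discontinued: 0.20 × 526 = 105.
- Surveys missing: 0.40 × 526 = 210.

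The 105 are not split by reason, so the number whose collection ended by an investigator's decision is between 0 and 105 (0 to 20%). Even at the upper end, 210 − 105 = 105 missing surveys have some other cause.

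**4. Precision at stake** (no design effect)

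| Surveys recovered | Evaluable | Pain interference | Physical function |
|---|---|---|---|
| 0 | 316 | 87.5% | 42.7% |
| 105 | 421 | 94.8% | 53.6% |

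The second row is a ceiling. It needs all 105 to have been withdrawn by investigators and all of them to respond.

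**5. Possible bias in PROMIS**

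Let m be the share of an arm whose collection was ended and g the observed mean minus the mean in that group. Its contribution to bias in the completer contrast is m₂g₂ − m₁g₁. The values of g are assumptions.

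- Equal m and equal g: 0.
- m = 0.20 in both arms (the ceiling), g differing between arms by 2 to 5 points: 0.20 × 2 = 0.4 to 0.20 × 5 = 1.0 points, against a minimally important difference of 2 for physical function.
- Smaller m shrinks this in proportion; at m = 0 it vanishes.

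The planned mixed model uses baseline and 6-month scores and would remove some of this bias if they predict the missing values.

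**The case against.** The strongest reply is that little was lost in practice. Section 3.13 attaches a label and stops no survey. Contact details of all randomised participants go to the coordinating centre (3.9.2), surveys are scheduled from the randomisation date (9.3), and SAP 8.1 says non-attenders were still invited. This stands: for people who merely stop attending, the defect is one of definition.

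Four stronger readings are tempting and are not supported.

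- **That the SAP keeps following people who newly meet an exclusion criterion.** It does not. The stop clause in SAP 4.6 ends surveys and EHR for those found ineligible or withdrawn by the investigator. The conflict with 3.12 for this group is about EHR only.
- **That dropping out of CBT or SDM is itself a ground for withdrawal.** Section 3.12 names disease progression that forces the intervention to stop, not voluntary drop-out. The list is permissive, and an exclusion criterion counts only if it rules out further participation.
- **That loss is unequal by arm.** The exclusion "Currently receiving CBT" could newly apply to an Arm 1 participant who takes up CBT, whereas CBT is the assigned treatment in Arm 2. But withdrawal is discretionary, SAP 4.7 and 9.2 plan to record psychotherapy and CBT use on the follow-up surveys, and neither document gives figures by arm.
- **That safety follow-up disappears.** Opioid- and suicide-related visits also come from the adverse event form and the EHR, and deaths also from the National Death Index and public data. The loss is partial, but the EHR back-up itself ends for investigator-withdrawn participants if SAP 4.6 is followed.

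SAP 8.1 also limits the reporting harm, because the flow diagram will show active withdrawals and early discontinuations with reasons.

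**Conclusion.** The point holds in two parts. First, the loss-to-follow-up definition in Protocol 3.13 conflicts with Protocol 3.9.2, SAP 4.6, SAP 8.1 and the intention-to-treat principle. This affects classification and reporting; the documents do not show that it cost any surveys.

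Second, Protocol 3.12 and the SAP 4.6 stop clause, as written, end outcome collection for randomised participants on grounds that an investigator decides and that are plausibly related to outcome. They also contradict each other on EHR data for the same people.

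The size is bounded but unknown: 0 to about 105 of 526. At the ceiling, physical function power would move from 42.7% to 53.6% and pain interference from 87.5% to 94.8%, and PROMIS bias could reach 0.4 to 1.0 points under the assumed differences. The true figures are probably lower, because the 105 may include people who left at their own request. A reader might attribute the whole 40% survey shortfall to ended contact, or assume a fixed share of the 105; the documents support neither.

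**What to change.** Leave the grounds for stopping the intervention to the investigators. Then:

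1. In Protocol 3.12 and 3.13 and SAP 4.6, record two separate statuses: *intervention stopped*, where T2, T3, EHR and safety collection continue unless the participant declines; and *participant withdrew from study contact*, where the addendum is offered.
2. Define loss to follow-up as unreachable after the hard-to-reach steps in 3.9.2, regardless of attendance.
3. Reconcile 3.12 with SAP 4.6 on surveys and EHR after investigator withdrawal, in both documents together, so that withdrawal from the intervention does not by itself end outcome collection. Editing the protocol alone would create a new conflict with the SAP stop clause.
4. Report survey missingness by arm and reason, separating the participant's own request, investigator decision, ineligibility and non-response.

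The cost is wording in two documents, one status field and a few more surveys. SAP 4.6 expected the last T3 survey in March 2023 and SAP 6 already cites June 2023 data, so surveys not sent are probably beyond recovery. Reclassifying the recorded reasons, settling the EHR rule for the final extraction and reporting by arm remain possible and cost little.

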## 4 STUDY EVALUATIONS AND MEASUREMENTS

### 4.1 Efficacy Evaluation

#### 4.1.1 Primary Outcome

**Opioid dose**, as measured by prescribed milligrams of daily MED, is the primary study outcome. The primary outcome will be examined at baseline and months 6, 12, and 18 using opioid prescription data (**Table 3**). Prescribing data (including drug name, start and stop dates, dose, and frequency) will be derived from the EHR and provided by the PCORnet STAR CRN warehouse common data model (CDM). The field generally accepts prescribing data as documenting ingestion; other current and previously published studies also use prescribed dose as the primary endpoint. However, we recognize that ingestion may not be the same as the prescribed regimen. We will analyze the absolute (primary) decrease (or increase) in opioid MED from the baseline period (average of 90 days prior to randomization) until 18 months after randomization. We also will examine percentage decrease. Total morphine equivalents for each prescription will be calculated by multiplying the quantity of each prescription by the strength of the prescription (milligrams of opioid per unit dispensed). The quantity-strength product is then multiplied by conversion factors derived from published sources to estimate the milligrams of morphine equivalent to the opioids dispensed in the prescription. The total average dose in morphine equivalents per day supplied is calculated by summing the morphine equivalents for each prescription filled during a given period and dividing by the number of days supplied.

#### 4.1.2 Secondary Outcomes

The 2 secondary study outcomes, **physical function** and **pain interference**, are based on patient self-report (**Table 3**). These outcomes will be examined at baseline and months 6 and 12. They will be measured using validated scales that are widely recognized in the pain literature as core outcomes. Both of the secondary outcomes were selected with input from patients and in consultation with pain experts, and they are part of the Patient-Reported Outcomes Measurement Information System (PROMIS). PROMIS is a set of patient-centered measures that evaluates and monitors physical, mental, and social health in adults and children. The PROMIS pain interference (PROMIS-PI) is an 8-item assessment of the extent to which pain interferes with daily functioning. It is a standard outcome in pain clinical trials and has excellent reliability and construct validity. The PROMIS physical functioning (PROMIS-PF) is an 8-item assessment of self-reported capability of general physical functioning over the past week rather than actual performance of physical activities. It is considered by experts to be a standard for comparative effectiveness research in chronic pain.

**Table 3. Primary and Secondary Outcomes**

Domain	Outcome	Data Source	Title	# Items	Timepoints	Description
Primary outcome: Clinical measure	Opioid dose	PCORnet STAR CRN warehouse data derived from electronic health records	n/a	n/a	Baseline and months 6, 12, and 18	Average daily opioid dose in milligrams of morphine equivalent (MED).
Key secondary outcomes: Patient Reported Outcomes (PROs)	Pain interference	Patient survey	PROMIS Short Form v1.0 – Pain Interference 8a	8	Baseline and months 6 and 12	Assesses self-reported consequences of pain on relevant aspects of one's life. 5-point Likert scale. 
	Physical function	Patient survey	PROMIS Short Form v1.0-- Physical Function 8a	8	Baseline and months 6 and 12	Assesses self-reported capability rather than actual performance of physical activities. 5-point Likert scale. 

Note: MED = morphine equivalent dose; PROMIS = Patient-Reported Outcomes Measurement Information System

#### 4.1.3 Other Self-Reported Outcomes

We will obtain additional self-reported outcome measures regarding pain intensity (both verbal 5-point Likert scale and numeric 10-point scale ratings) and numeric rating of physical function using the PROMIS pain intensity scale and may also use the 11 validated items of the Brief Pain Inventory (BPI) (Table 4). Using both verbal and numeric ratings is recommended in the literature as an outcome measure for trials of chronic pain treatments. Doing so makes it possible to compare results across studies and limits the amount of missing data that results if some patients have difficulty completing one of the ratings.

Chronic pain is often accompanied by emotional distress, anxiety, and depression, and for this reason, we will measure anxiety and depressive symptoms at baseline, 6, and 12 months using PROMIS measures.

Intent to taper will be measured via self-report at baseline and months 6 and 12. The follow-up assessments at months 6 and 12 will also include a self-report measure of relative opioid use (no longer taking opioids, higher dose than baseline, or lower dose than baseline).

Covariates will include demographic characteristics, health insurance status, health literacy level, and patient-centered communication. Age, gender, race, and ethnicity will be included on the baseline survey. These self-report variables will be cross-referenced to EHR-derived data to confirm alignment of the two data sources.

**Table 4. Additional Self-Reported Outcome Measures**

Measure	Title	# Items	Timepoints	Description
Pain Intensity (verbal rating)	PROMIS Scale v1.0 Pain Intensity 3a short form	3	Baseline, months 6 and 12	Assesses how much a person hurts using a 5-point Likert scale. The first two items assess pain intensity over the past seven days. The last item asks patients to rate their pain intensity "right now." 
Pain Intensity (numeric rating)	Brief Pain Inventory (BPI) – pain intensity sub-scale	4	Baseline, months 6 and 12	These items ask about level of pain over the past week, with responses on a numeric scale of 0 to 10. 
Pain Interference (numeric rating)	Brief Pain Inventory (BPI) pain interference sub-scale	7	Baseline, months 6 and 12	These items ask about pain interference over the past week, with responses on a numeric scale of 0 to 10. 
Emotional distress (Anxiety)	PROMIS—Anxiety, 4-item Short Form	4	Baseline, months 6 and 12	Assesses generalized anxiety/distress over the past 7 days. 5-point Likert scale. 
Depressive symptoms	PROMIS Short Form v1.0 – Depression 4a	4	Baseline, months 6 and 12	Assesses depressive symptoms over the past 7 days. 5-point Likert scale. 
Demographic characteristics	n/a	8	Baseline	Age, race, ethnicity, assigned sex at birth, gender identity, education, marital status, and employment status
Health insurance status	n/a	1	Baseline, months 6 and 12	This item assesses if a patient has health coverage and what type
Health literacy	Health Literacy Skills Instrument (HLSI)	4	Baseline	Assesses the patient's understanding of health information.
Patient-centered communication	Patient-centered communication	6	Baseline, months 6 and 12	Assess the patient's experience with care and communication

